### 4.5. Demographic and Baseline Characteristics

Subject demographics including gender, ethnicity, race, age (years), baseline weight (kg), height (cm), and body mass index (BMI) ( $\text{kg}/\text{m}^2$ ) will be tabulated. The baseline disease characteristics including pulmonary function (Forced Expiratory Volume in 1 second in Liters (FEV1 (L)), percent predicted FEV1 (ppFEV1) (%), Sweat Chloride (mmol/L), and CFQ-RSS (only applicable in MAD cohort) will be summarized.

Data will be summarized by dose group and overall for subjects in the safety population. Display may be repeated with the exploratory analysis population if the exploratory analysis and safety populations differ.

Height (in cm) = height (in inches) \* 2.54

Weight (in kg) = weight (in lbs) \* 0.4536

BMI (kg/m^2) = Weight (kg) / [Height (m^2)]. BMI at each visit will be calculated using weight at the visit and height from the screening visit

ppFEV1 (%) = percent predicted FEV1 (with a unit of percentage points) is the ratio of FEV1 (L) to the predicted FEV1 (L), expressed as a percentage. The predicted FEV1 (L) is computed using the NHANES III normal value (REFERENCES

Hankinson et al., Spirometric Reference Values from a Sample of the General U.S. Population, (1999), AMERICAN JOURNAL OF RESPIRATORY AND CRITICAL CARE MEDICINE, VOL 159 179-187 ) according to gender, race, age & height.

Demographic and Baseline data will be provided in data listings.

#### **4.6. Medical History**

Medical History will be summarized by dose group and overall for the safety population. Outputs may be repeated for the exploratory analysis population if exploratory analysis and safety populations differ.

#### **4.7. Treatment Compliance and Extent of Treatment Exposure**

Study drug will be administered in the clinic by qualified site personnel, by inhalation via the designated study nebulizer, until all study drug solution has been administered. Complete administration of study drug/placebo, if uninterrupted, should take approximately less than 20 minutes.

Treatment compliance and extent of exposure will be summarized by treatment group and overall, including time on study, number of study doses completed, number of subjects that completed dose at each dose visit, number of device pauses, status of full dose delivery, and nebulization duration at each dose visit. A listing of treatment exposure will be provided.

Treatment compliance will be presented for the safety population.

Outputs may be repeated for the exploratory analysis population if exploratory analysis and safety populations differ.

Time on study is defined as end of study date – first dose date +1. See section 4.2.4 for definition of end of study date.

For dose-visit dates, please refer to Section 4.2.7.

#### **4.8. Exploratory Efficacy Evaluation**

Efficacy analyses will be conducted using the exploratory analysis population.

##### **4.8.1. SAD**

The exploratory efficacy evaluations will include the following endpoints.

##### **4.8.1.1. ppFEV1 (%)**

The ppFEV1 value, absolute change from baseline and % change from baseline (relative change) will be presented descriptively over time (considering all time points from the visit windows for this parameter), per treatment group.

Graphical representation may be provided (mean change+ 95% CI overtime). Particularly a zoom on the data for the first 24 hours following first dose will be given).

[figure not shown]
In order to assess differences versus placebo a mixed model with repeated time measures on the change from baseline ppFEV1 as outcome variable and including treatment, baseline ppFEV1 value, time and interaction between time and treatment as covariates. By default, an unstructured covariance matrix will be used, unless convergence issue, in which case other covariance matrix will be explored. Adjusted means and corresponding confidence interval will be presented.

For Day 1, several spirometry assessments (pre and post dose) are planned. Subjects usually suffer from fatigue due to the multiple assessments, resulting in low post-dose values of FEV1. Additionally, inhalation of the IMP may transiently impact the spirometry results. Thus the following time points will be included in the repeated measures analysis: Baseline, Day 2, Day 4 and Day 8, using the time windows.

Analyses to explore the dose response using the MCPMod methodology will be followed. A set of dose-response models will be tested including change from baseline ppFEV1 at Day 4 as dependent variable, the treatment as factor (0, 6.25, 12.5, 25, 50 mg) and ppFEV1 value at baseline (see Table 25 and Figure 2). The presence of a dose-response signal will be demonstrated if at least one of the candidate models is significant, adjusting for the different models (overall alpha=5% two-sided). Due to the small sample size, overall alpha for this exploratory dose-response analysis may be adapted. If a model is selected, an estimate of the minimum effective dose will be performed. Thresholds of 3%, 5% and 7% will be tested as sizes of interest of treatment effect (differences versus placebo).

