4.2 Study Design

The study is a multicenter, randomized, double-blind, and placebo-controlled Phase 1b SAD and MAD design. The subject, investigator, and site personnel (except pharmacist) will be blinded to treatment, while the sponsor will be unblinded. Sponsor personnel will be unblinded to subject

treatments in order to permit real-time interpretation of the safety, pharmacokinetic, and pharmacodynamic data. The site monitor will remain blinded to individual subject treatment allocation until all monitoring of study data has been completed. To minimize the potential for bias, individual subject treatment randomization information will not be released to the investigator or blinded study site personnel until the study database has been locked.

Eligible subjects with homozygous $\Delta F508$ CF will be randomized at a 3:1 ratio to receive either QR-010 or placebo via oral inhalation (nebulization). This study will be conducted in North America and select European countries.

[figure not shown]
The study includes 2 stages. The first stage is a single ascending dose-escalation (SAD) design to determine safety and tolerability of a single dose of QR-010. The second stage is a multiple ascending dose escalation (MAD) design to further assess the safety, tolerability, and exploratory efficacy of 12 doses of QR-010 over 4 weeks. All doses will be administered in a clinical setting.

For the SAD cohorts, subjects will receive the dose in an inpatient observation unit and be observed for a total 4 days, and will be discharged on Day 4. Subjects will return for PK and safety follow-up as an outpatient on Day 8 (End of Study Visit).

For the MAD cohorts, subjects will receive doses 1 through 12 in a clinic while under observation. On Day 1 and Day 3 subjects will be observed until 12 hours post dose. Following the last dose (dose 12), subjects will return twice for PK sampling, and will be evaluated 7 and 28 days after the last visit for this additional safety monitoring and sampling for PK.

A schematic of the study design is presented in Figure 3.

Figure 3: PQ-010-001 Study Schematic

Single Ascending Dose Escalation Cohorts: The first two subjects of each cohort may be dosed on the same day, at least 4 hours apart. If no significant AEs occur, the remainder of the cohort may be dosed at least 24 hours later, with at least 1 hour between subjects.

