### 2.5.2. Unblinding

The DSMC is unblinded to the Study Treatment. Safety data from each cohort will be provided unblinded and evaluated by the DSMC at the end of each cohort, prior to escalation to the next dosing level. Additionally if AEs of interest occur at a Grade 2 level or higher, as defined in the protocol, they will be provided to the DSMC for evaluation in a timely fashion (i.e., without waiting for completion of the cohort) to support dose escalation decisions and determination of dose limiting toxicity events.

Sponsor personnel may be unblinded to subject treatments in order to permit interpretation of the safety, pharmacokinetic, and pharmacodynamic data. The site monitor will remain blinded to individual subject treatment allocation until all monitoring of study data has been completed. To minimize the potential for bias, individual subject treatment randomization information will not be released to the investigator or blinded study site personnel until the study database has been locked.

In the event of a medical emergency, when knowledge of treatment assignment is needed for immediate medical management of the subject's health, Investigators can obtain unblinded treatment assignment through the centralized IWRS system at any time. Thorough documentation of the rationale for unblinding is required. Consultation of the study Medical Monitor is recommended for all unblinding requests.

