#### 4.2.6. Multiple Comparisons/Multiplicity

Due to the exploratory nature of the study, all tests for exploratory efficacy are conducted at alpha level 5%, two-sided (or 2.5% one-sided), and there will be no adjustment for multiplicity.

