### 4.3. Interim Analyses

Safety will be assessed prior to each dose escalation by the DSMC.

For development purposes data analyses may be performed during the study.

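### SAP 4.8.1.1 fixes 5% for declaring a ppFEV1 dose-response signal, then lets that level change with no value, limit or timing, so the false-signal rate is 5% only if the option goes unused

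*SAP*

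**What the plan says.** **Decision rule (SAP 4.8.1.1, SAD ppFEV1 at Day 4).** "The presence of a dose-response signal will be demonstrated if at least one of the candidate models is significant", with significance judged after "adjusting for the different models (overall alpha=5% two-sided"). If a model is selected, a minimum effective dose is estimated, with 3%, 5% and 7% as the differences from placebo of interest.

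**Permission to move the level (same paragraph).** "Due to the small sample size, overall alpha for this exploratory dose-response analysis may be adapted". Nothing further is said about the new level.

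**Reach.** SAP 4.8.2.1 applies the SAD method by cross-reference to MAD ppFEV1 at Day 26 pre-dose, Day 26 four hours post-dose and Day 33.

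**General rule (SAP 4.2.6).** "all tests for exploratory efficacy are conducted at alpha level 5%, two-sided (or 2.5% one-sided), and there will be no adjustment for multiplicity".

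**Who can see what, and when.** Protocol 4.2 blinds the subject, the investigator and site staff other than the pharmacist, "while the sponsor will be unblinded". SAP 2.5.2 is softer: "Sponsor personnel may be unblinded to subject treatments in order to permit interpretation of the safety, pharmacokinetic, and pharmacodynamic data". SAP 4.3 adds: "For development purposes data analyses may be performed during the study", and Protocol 13.11 says the same.

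**The concern.** A significance rule means something because its threshold is set without reference to the result. Here the threshold is stated and then released. No text requires the level to be settled before treatment-coded ppFEV1 results are looked at, and the people who would settle it may hold those results.

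The stated reason, small sample size, does not explain leaving the level open. The plan of 8 subjects per cohort and 32 per part was known from the start (Protocol 13.2, SAP 4.1), so a larger exploratory level could have been written down as a number.

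At stake is how a positive finding can be read. The test decides whether a minimum effective dose is estimated, and that estimate could inform later studies. If the level may rise to meet the observed p-value, the test no longer screens out chance patterns, yet the SAP's verb for a positive result is *demonstrated*.

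**Working it through.** **1. Inputs.** Doses 0, 6.25, 12.5, 25 and 50 mg. Each part has four cohorts of 6 active and 2 placebo (SAP 4.1), so pooling placebo gives groups of 8, 6, 6, 6 and 6, N = 32. Table 25 lists five candidate shapes: linear, log-linear, Emax (ED50 25), exponential (scale 12.5) and logistic (ED50 25, scale 3). One baseline covariate gives df = 32 − 5 − 1 = 26. The SAP does not state the log-linear offset, so I tried 0.5, 1 and 5.

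**2. Method.** For each shape with group means m_i, the contrast weights are proportional to n_i(m_i − m̄), where m̄ is the n-weighted mean. The statistic is the largest |t| over the five contrasts. Its null distribution is multivariate t with 26 df and the correlations implied by the contrasts, simulated with 1,000,000 draws. The critical value c satisfies P(max|t| > c) = α, and was checked on a fresh set of draws.

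**3. The plan's own figure reproduces.** At 5% two-sided, c is 2.41, 2.39 and 2.35 for the three offsets. The type I error on fresh draws is 4.97% to 5.05%, which is 5% within simulation error. A one-sided 2.5% test gives the same cut-offs.

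**4. If the level is changed.** The 10%, 20% and 30% rows are illustrations.

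| Overall α (two-sided) | Critical max\|t\| across offsets | False-signal rate per run |
|---|---|---|
| 5% (SAP) | 2.35 to 2.41 | 5% |
| 10% (assumed) | 2.00 to 2.06 | 10% |
| 20% (assumed) | 1.61 to 1.67 | 20% |
| 30% (assumed) | 1.36 to 1.42 | 30% |

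With offset 0.5, a result between 1.67 and 2.06 is no signal at 5% or 10% and a signal at 20%.

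**5. If the level is chosen after the result.** Suppose the analyst would accept any level up to L. Under the null, a signal is declared whenever p ≤ L, so P(false signal) = L, even if 5% was tried first. The SAP sets no L.

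**6. Is there a pull to relax it?** The documents give no SD, so SDs of 5, 7.5 and 10 points are assumed. For a true linear trend reaching 5 points over placebo at 50 mg (offset 0.5), power is:

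| α | SD 5 | SD 7.5 | SD 10 |
|---|---|---|---|
| 5% | 45% | 23% | 15% |
| 10% | 58% | 34% | 24% |
| 20% | 73% | 49% | 38% |

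A miss at 5% is more likely than not across this range, which is when the option would be attractive.

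**The case against.** **It is exploratory.** Protocol 13.4 treats any inferential statistics as hypothesis generating, the synopsis says p-values will be read in that light, and the study is not powered for efficacy. Escalation and the MTD rest on DLTs reviewed by the DSMC, not on the minimum effective dose. All of this stands and caps the importance of the point. It does not supply the missing level, and it argues against *demonstrated*.

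**The 5% holds unless someone changes it.** This stands. A reader might infer that the signal claim has no error rate at all; the SAP does not support that, because 5% is the stated default and is attainable. The loss is conditional on the option being used.

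**SAP 4.2.6 is not contradicted.** A specific provision can depart from a general rule, and 4.8.1.1 already does so by adjusting across candidate models while 4.2.6 says "there will be no adjustment for multiplicity". That is fair: this is an exception the SAP does not acknowledge, not a clash of two binding rules.

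**Not every dose-response test is affected.** A reader might extend the permission to glucose, CFQ-R RSS and weight. Those sections name the MCPMod method without the cross-reference used for MAD ppFEV1, and the sentence concerns one analysis, so on a plain reading 4.2.6 governs them. Nor should the point be sized by the chance of any false signal across all planned runs. That mostly measures the SAP's open choice not to adjust across endpoints, which exists at 5% and would survive deletion of the sentence; it also needs an independence assumption that runs sharing subjects do not meet.

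**Unblinding is a declared design feature**, intended for interpreting safety, PK and PD data. Nothing shows an intention to tune the level. The point is only that the plan does not prevent it.

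**Conclusion.** The concern holds in a limited form. SAP 4.8.1.1 states a valid 5% rule and then grants an unbounded, untimed permission to change it, in a trial where the sponsor is unblinded and may analyse data along the way. Used as written, that permission replaces the stated 5% per-run false-signal rate with the level finally accepted: 10% at 10%, 20% at 20%. Those levels are assumptions; the 5% is the SAP's and is confirmed by simulation under the planned allocation and the offsets tried.

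Four planned runs are affected: one SAD and three MAD ppFEV1 analyses, together with the minimum-effective-dose estimate each can trigger. The safety, DLT and MTD conclusions are untouched. The point is minor, but it is more than a missing detail, because the text grants a permission that removes control of the error rate.

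**What to change.** In SAP 4.8.1.1, delete the sentence allowing the level to be adapted, and keep 5% two-sided (2.5% one-sided) as in 4.2.6. SAP 4.8.2.1 then inherits the fixed level.

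If a larger exploratory level is wanted, state one number and its sidedness, say that it is an exception to 4.2.6, and fix it before any unblinded ppFEV1 data from either the SAD or the MAD part are analysed. Fixing it only before the MAD data would be too late for the SAD analysis to which the sentence belongs. Report any later change as post hoc, alongside the 5% result.

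Replace *demonstrated* with *suggested*.

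The cost is one sentence removed, or one number added, and one word changed. No data collection, sample size or safety analysis is affected. At 5% power may be low, as the second table shows, but that follows from the sample size and is better reported than absorbed by a movable threshold.

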**Table 25: Set of Candidate Models for Dose-Response**

Model	Parameters	
	ED 50	Scale $\delta$
Linear	-	-
Loglinear	-	-
E max	25	-
Exponential	-	12.5
Logistic	25	3

**Figure 2: Candidate model for ppFEV1 dose response**

4.8.1.2. FEV1 (L)

FEV1 value, change from baseline and % change from baseline will be presented descriptively over time, per treatment group. Graphical representation may be provided.

4.8.1.3. FVC (L)

FVC value, change from baseline and % change from baseline will be presented descriptively over time, per treatment group.

4.8.1.4. FEF25/75 (L)

FEF25/75 value, change from baseline and % change from baseline will be presented descriptively over time, per treatment group.

4.8.1.5. C-Reactive Protein (CRP) (mg/L)

CRP value and change from baseline will be presented descriptively over time, per treatment group. Graphical representation may be provided (mean +95% CI overtime).

4.8.1.6. Erythrocyte Sedimentation Rate (ESR) (mg/L)

ESR value and change from baseline will be presented descriptively over time, per treatment group. Graphical representation may be provided (mean +95% CI overtime).

#### 4.8.2. MAD

##### 4.8.2.1. ppFEV1 (%)

The ppFEV1 value, absolute change from baseline and % change from baseline (relative change) will be presented descriptively over time (considering all time points from the visit windows for this parameter), per treatment group.

Graphical representation may be provided (mean change+ 95% CI overtime). Particularly a zoom on the data for the first 24 hours following first dose will be given).

In addition, the SAD and MAD ppFEV1 for the first 24 hours will be pooled in order to provide more robust data to the first day evolution.

The mixed-model analysis will be performed with repeated time measures on the change from baseline ppFEV1 as outcome variable and including treatment, baseline ppFEV1 value, time and interaction between time and treatment as covariates. By default, an unstructured covariance matrix will be used, unless convergence issue, in which case other covariance matrix will be explored. Adjusted means and corresponding confidence interval will be presented.

For visits with a dose, several spirometry assessments (pre and post dose) are planned. Subjects usually suffer from fatigue due to the multiple assessments, resulting in low post-dose values of FEV1. Thus the following time points, concentrating on the pre-dose evaluations during treatment, and the post-treatment time points will be considered: Baseline, Day 3 pre-dose, Day 4, Day 5 pre-dose, Day 8 pre-dose, Day 15 pre-dose, Day 22 pre-dose, Day 26 pre-dose, Day 26 4 hours post-dose, Day 33 and Day 54. Differences versus Placebo will be estimated at Day 26 pre-dose, Day 26 4 hours post-dose, Day 33 and Day 54.

A sensitivity analysis including presence/absence of *Pseudomonas aeruginosa* at Baseline as a covariate will be performed.

Analyses to explore the dose response using the MCPMOD methodology as described in the SAD section will be followed. The change from baseline in ppFEV1 at Day 26 pre-dose, Day 26 4 hours post-dose and Day 33 will be assessed.

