## **4. STATISTICAL METHODS**

### **4.1. Sample Size Justification**

This is a Phase 1 safety study designed to evaluate the safety, tolerability and PK of QR-010. The sample size is not based on power calculations. It is chosen based on clinical experience and considered to be adequate to fulfill the objectives of the study.

Approximately 64 subjects will be enrolled in the study, with 8 subjects per cohort (6 QR-010 and 2 placebo), 32 each in the SAD and MAD portions of the study. The exact number of subjects enrolled is dependent on whether any dose levels are to be expanded due to the occurrence of AEs of interest.

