## 3. ANALYSES

### 3.1. ppFEV1 (%)

Descriptive summaries will be performed on Per Protocol Populations and Sensitivity Population excluding outliers of PPFEV1. Summaries will be repeated on subgroups of PPFEV1 at baseline for the 3 populations.

The mixed-model analysis described in the SAP will be repeated on the Per Protocol and Sensitivity Populations (using the following time points: Baseline, Day 4, Day 5 pre-dose, Day 8 pre-dose, Day 15 pre-dose, Day 22 pre-dose, Day 26 pre-dose, Day 26 4 hours post-dose, Day 33 and Day 54. Differences versus Placebo will be estimated at Day 15, Day 26 pre-dose, Day 26 4 hours post-dose, Day 33 and Day 54). Differences versus Placebo at Day 15 will also be assessed on Exploratory Population (in addition to planned time points).

The mixed model analysis will also be carried out on subgroups of PPFEV1 at baseline for the 3 populations. Due to the small sample size, the following time points only will be included in the model: Day 15 pre-dose, Day 26 pre-dose and Day 33.

The sensitivity analysis including presence/absence of *Pseudomonas aeruginosa* at Baseline as a covariate will be repeated on Per Protocol Populations. Day 15 will be added as time point of interest for both Exploratory and Per Protocol Populations.

Analyses to explore the dose response using the MCPMOD methodology as described in the SAP will be followed and repeated on Per Protocol Populations. The change from baseline in ppFEV1 at Day 15 pre-dose (also on Exploratory Population), Day 26 pre-dose, Day 26 4 hours post-dose, Day 33 and Day 54 will be assessed.

In addition to the dose-responses shapes described in the SAP, a quadratic model with umbrella-shape will be tested. Parameters of the dose-responses shapes models may be adapted to fit the data.

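### The SAP mixed models name no small-sample df or standard-error method and leave the covariance fallback open; MAD ppFEV1 (45 covariance parameters, 32 subjects) is the most exposed

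*SAP*

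**What the plan says.** SAP 4.1 plans "8 subjects per cohort (6 QR-010 and 2 placebo), 32 each in the SAD and MAD portions of the study" and adds that "The sample size is not based on power calculations". SAP 4.8.1.1 lists treatment with five levels, "the treatment as factor (0, 6.25, 12.5, 25, 50 mg"), and Table 4 has a single pooled placebo column.

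The MAD ppFEV1 model in SAP 4.8.2.1 takes change from baseline as outcome, with treatment, baseline, time and time-by-treatment. On covariance it says: "By default, an unstructured covariance matrix will be used, unless convergence issue, in which case other covariance matrix will be explored". It lists ten post-baseline time points, from Day 3 pre-dose to Day 54. Contrasts with placebo are planned at Day 26 pre-dose, Day 26 four hours post-dose, Day 33 and Day 54.

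Near-identical wording serves SAD ppFEV1 (4.8.1.1), glucose (4.8.2.8), CFQ-R RSS (4.8.2.9) and weight (4.8.2.10). Those models have three post-baseline visits, or five for glucose. SAP 4.2.6 says that "all tests for exploratory efficacy are conducted at alpha level 5%, two-sided (or 2.5% one-sided), and there will be no adjustment for multiplicity". SAP 4.2.10 names SAS and R but no procedure or options.

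The post hoc addendum (3.1) repeats the ppFEV1 model in further populations, without Day 3. For baseline subgroups it cuts the model to three visits: "Due to the small sample size, the following time points only will be included in the model".

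**The concern.** Two decisions that affect the error rate are left open.

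The first is the reference distribution. Model-based standard errors treat the estimated covariance as known. With this many parameters and this few subjects, that understates uncertainty, and a normal reference adds to the problem. The addendum recognises the small sample, but only in subgroups and only by dropping visits.

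The second is the fallback. It allows any structure, picked after the fit has been seen, and protocol 4.2 has sponsor personnel unblinded during the study. A homogeneous structure forces one variance on Day 4 and Day 54 alike. If variability grows over time, late intervals come out too narrow and early ones too wide.

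At stake are the stated 5% level and the confidence intervals for the placebo differences. Protocol 4.1.3 says that the observed changes may inform the design of future studies.

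**Working it through.** **Plan's own figures.** 4 cohorts x 8 = 32 MAD subjects: 4 x 2 = 8 placebo and 6 per dose. This reproduces. The SAP gives no power figure, SD or dropout rate.

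**Model size.** Baseline is on the list of time points, but its change is zero by construction, so only post-baseline visits count. Protocol 7.4.4 schedules no pre-dose spirometry on Day 3, so nine of the ten listed visits are collectable.

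- Covariance parameters, k(k+1)/2: 9 x 10/2 = 45 (ten visits: 10 x 11/2 = 55).
- Fixed effects: 5 x 9 + 1 = 46 (ten visits: 51).
- Between-subject df: 32 - 5 - 1 = 26, critical t = 2.056.

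**Anchor.** With complete data and no baseline covariate, the variance at one visit has 32 - 5 = 27 df. Using 1.96 gives P(|t27| > 1.96) = 6.04%, or 6.08% on 26 df. A normal reference alone therefore costs about one point.

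**Simulation under no effect.** Arms 8, 6, 6, 6, 6; nine visits; REML; 2,500 trials per scenario; four doses against placebo at the four late time points. Assumed, because the documents give nothing: 0% or 15% monotone dropout and five true covariances (compound symmetry; subject effect plus exponential decay with a 14-day or 30-day range; random slopes; random walk). Monte Carlo SE is roughly 0.3-0.5 points per visit, more at the highest rates.

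Unstructured fit, averaged over late time points:

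| Reference | Error rate | By visit |
|---|---|---|
| Normal or residual df | 6.0-6.8% | 5.5-6.9% |
| 26 df or Satterthwaite | 5.0-5.6% | 4.7-5.8% |
| Kenward-Roger | 5.0-5.2% | 4.7-5.4% |

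Compound symmetry fitted to the same data, normal or residual df:

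| True covariance | Day 33 | Day 54 |
|---|---|---|
| Compound symmetry | 5.1-5.4% | 5.2-5.3% |
| Exponential decay | 8.0-10.2% | 9.3-13.6% |
| Random slopes or random walk | 7.6-9.4% | 14.9-19.7% |

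Using 26 df trims these only in part: the decay case at 13.6% falls to 11.9%. The unstructured fit converged in 99.9-100% of replicates.

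**Rising SD (assumed: SD of change 4 to 7, visit correlation about 0.45-0.95).** With 26 df, the unstructured Day 33 and Day 54 tests ran at about 5% with complete data, 5.4-6.2% at 15% dropout and 6.0-7.0% at 25%. A separate rising-SD run at 15% dropout gave 5.4-5.6% at late visits with 26 df and 6.5-6.8% with a normal reference. Across the two runs at 15% dropout, compound symmetry gave 9.3-9.7% at Day 33, 11.8-12.1% at Day 54 and 0.6% at Day 4. With constant SD it gave 4-5%.

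**Addendum subgroups (assumed n = 16, three visits).** Default standard errors gave 6.4-8.2%; Kenward-Roger gave 5.5-6.4%.

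**Candidate fallbacks (rising SD, 15% dropout).** Heterogeneous Toeplitz and AR(1) indexed by visit order gave about 7% at Day 4 and 2-3% at Days 33 and 54. Heterogeneous compound symmetry gave 3.8-5.6%.

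**The case against.** A reader might infer that the planned tests simply run at 5.5-7%, or at 9-12% at late visits. The documents support neither as a flat statement. The SAP is silent on df; it does not choose a liberal reference, and with 26 df the excess at up to 15% dropout is about half a point. Dropout is also assumed. Protocol 13.3.3 allows replacement of early discontinuers, and 7.4.12 asks them back for the End of Treatment and End of Study visits, both with spirometry; the simulations did not build these in. The late-visit inflation needs the unstructured fit to fail, a homogeneous structure to be picked, and a truth that differs from it.

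Nor do nine visits describe every mixed model; that count belongs to MAD ppFEV1. No error rates were computed for the other full-sample models.

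The consequence is limited as well. Protocol 13.4 treats any inferential result as hypothesis generation, and SAP 4.2.6 makes no multiplicity adjustment. The primary endpoints (adverse events and DLTs) are untouched.

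All of this stands and limits the size of the point. It does not remove the gap. Fit failure is also less remote than the simulations suggest. They used regularly collected visits, whereas SAP 4.8.2.1 includes Day 3 pre-dose, and Table 7 gives it a window although the protocol schedules no such test. A few stray values spread over five arms would leave almost no information on that visit's variance.

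**Conclusion.** The point holds as a specification gap of minor-to-moderate weight. The SAP states no small-sample df or standard-error method for any mixed model and leaves the covariance fallback to choice after the fit is seen. For MAD ppFEV1 the choice of df alone moves the unstructured tests between about 5.0-5.6% and about 6-7%, with heavier dropout adding to this. A homogeneous fallback could leave late-visit tests near 5% or take them to about 8-14%, and beyond that at Day 54 if variance grows with time.

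The model dimensions rest on the documents. Every error rate rests on assumed covariances and dropout, and the fallback rates also on a failed unstructured fit and on a structure that the SAP does not name.

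**What to change.** Add to SAP 4.2 and apply to every mixed model, addendum included: *Models will be fitted by REML with Kenward-Roger standard errors and degrees of freedom. If the unstructured fit does not converge, heterogeneous compound symmetry will be used; if that does not converge, a structure with visit-specific variances and correlation depending on actual time between visits. The first to converge is final.*

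Structures indexed by visit order are best avoided. They treat the four-hour gap on Day 26 like the 21 days from Day 33 to Day 54. For the time-based structure, the four-hour gap must enter as 4/24 = 0.17 day, not zero.

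Also reconcile Day 3 pre-dose with protocol 7.4.4 (the addendum already omits it), and give Day 26 four hours post-dose its own window. Table 7 has none; its 60-minute window runs to Day 26 + 3 days.

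The cost is a short paragraph and one software option. Kenward-Roger raised the variance by about 5-8% in simulation, so standard errors grow by a factor of 1.025 to 1.039 (the square roots of 1.05 and 1.08). It does not fully restore 5% in the small subgroups, and the time-based second fallback was not simulated.
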